7.0. Project Timeline

Months 1-5 will be devoted to start-up activities, including confirming logistic arrangements, recruiting and training staff, and developing detailed procedures with prison and treatment personnel, and obtaining IRB and OHRP approval. Recruitment of participants and delivery of interventions will begin in month 6. Five to six prison inmate/participants are projected to be enrolled per month, yielding a total of 240 participants (120 per condition), at the end of recruitment (month 40). Follow-up assessments will be completed by month 53. Months 54-60 will be devoted to dissemination activities (e.g., publication of the primary outcomes paper).

8.0. Impact

This proposed intervention addresses several public health and public safety problems. First, it will likely impact the problem that a substantial number of prisoners with histories of OUD are released to the community and untreated by treating their addictions. Second, by eliminating transportation costs and time, and the requirement that reliable transportation is required for treatment adherence, the treatment comes to the patient rather than the patient must go to treatment. This is likely to improve adherence, which tends to reduce the possibility of addiction. Third, by substantially impacting addiction, in turn, it has increased chances of reducing death from overdose, HIV and hepatitis infection, the frequency of criminal activity, and the likelihood of re-incarceration.

9.0. PROTECTION OF HUMAN SUBJECTS

This Human Subjects Research involves an NIH-Defined Phase III Clinical Trial.

9.1. Potential Risks

9.1.1. Extended-Release Naltrexone (XR-NTX). Participants may experience brief withdrawal symptoms with the naloxone test, although this will be uncommon as only patients with a history of no opiate use and negative urine for opiates will be given the test. Those receiving an XR-NTX intramuscular injection may experience side effects consisting of pain at the site of injection, nausea, or other opioid withdrawal symptoms. In rare cases, an infection at the site of injection has occurred. XR-NTX has been reported to cause increased liver enzymes when it was given in high dose oral form, but this has not been reported with the dose used in the injection. Participants in both conditions carry the risk of relapse to opioid dependence, as is the case for all individuals who have a history of opioid use disorder. Relapse to opioid dependence after a detoxification and opioid-free period, or after discontinuing depot naltrexone, carries a risk of opioid overdose and death because tolerance after a period of abstinence is low. Participants will be informed of these risks and of treatment alternatives, including agonist maintenance.

XR-NTX injections will block the effects of opioid pain medication and all participants randomized to the naltrexone condition will receive a card to present in case of emergency need for opioid analgesia. General anesthetics, nerve blocks, and non-steroidal pain medications are not affected. All individuals who will be administered depot naltrexone will be informed as follows: **“You should carry identification to alert medical personnel to the fact that you are taking depot naltrexone. A depot naltrexone medication card has been supplied to you for this purpose. Carrying the identification card should help to ensure that you can obtain adequate treatment in an emergency. If you require medical treatment, be sure to tell the treating physician that you are receiving depot naltrexone therapy”**.

9.1.2. Other Risks. Other risks are expected to be minimal. Participants will be asked to provide sensitive information regarding a number of behaviors, including deviant and criminal behaviors, and are thus exposed to the risks associated with the potential for disclosure of confidential information outside the research context. Because participants will be discussing personal information, including information on psychological functioning, some participants may experience emotional discomfort.

9.2. Protection Against Risks

9.2.1. Risks Associated with XR-NTX. Participants may experience symptoms of opioid withdrawal from the naloxone challenge, oral naltrexone, or XR-NTX injection. In order to minimize the likelihood of withdrawal symptoms, potential participants will be carefully screened with exclusion criteria which include recent opiate use history and a urine test prior to naloxone administration. The study design was carefully crafted to minimize risk of withdrawal by first administering the short-acting naloxone followed by a small oral dose of naltrexone prior to XR-NTX administration. Individuals who do experience opiate withdrawal symptoms from the administered opioid antagonists will be treated symptomatically by the study’s medical personnel.

To protect against risks of increase in liver enzymes, study applicants will be excluded if their liver enzymes are greater than triple the normal levels. Also, liver enzyme tests will be repeated during the course of the study and doses withheld if indicated.

Participants will be warned of the risk of opioid overdose should they discontinue XR-NTX and will be informed of alternative treatment, including methadone or buprenorphine treatment. Finally, participants will be informed that they should carry their study identification card with them and provide it to any medical personnel that will be treating them in the future so they can be aware of the need to provide appropriate alternatives to opioids for pain relief.

The study physician has extensive experience in the injection technique. This should minimize the likelihood of injection site reactions. Nonetheless, the FDA has provided the following information for healthcare professionals with regard to Naltrexone Injection Site Reaction [naltrexone for extended-release injectable suspension (marketed as Vivitrol)] FDA Alert [08/12/08] Vivitrol injections may be followed by pain, redness, itching, bruising, and swelling. Sometimes reactions at the injection site can quickly worsen and skin and other tissue can be permanently damaged and require surgery. If an injection site reaction does not improve within two weeks following the injection, or it worsens sooner than 2 weeks, the participant will be instructed to see his/her doctor. The dose of Vivitrol® (380mg) selected for this research has been studied in both normal healthy adults as well as in individuals who were using opioids, alcohol, and stimulants.

9.2.2. Vivitrol (naltrexone for extended-release injectable suspension): Medication Guide Required for Patients. Some people on Vivitrol treatment have had severe reactions at the site of the injection (injection site reactions), including tissue death (necrosis). Some of these injection site reactions have required surgery. The participant will be instructed to seek medical attention immediately if he or she has any of the following things happen at any of the injection sites: intense pain; an open wound the area feels hard; a dark scab large area of swelling; lumps; and blisters. FDA requires that a Medication Guide, which communicates this and other important information about treatment, be provided to all participants.

9.2.3. Risks Associated with Loss of Confidentiality. To assure participant confidentiality, as in our previous and ongoing research, we will obtain a federal Certificate of Confidentiality to protect all data against subpoena and criminal justice investigation; we will provide training to all research staff regarding

responsibilities for maintaining and protecting participant confidentiality. To ensure confidentiality, we will use of unique participant identifiers in the database. Baseline and follow-up measures will be linked by the unique identifiers employed and will be stored in the locked files to which only the Principal Investigator, Co-Investigators, and Project Manager have access. Study findings will make use of aggregate data only and publication or presentation of findings will not involve use of any individual or personalized information.

9.2.4. Risk Associated with Emotional Discomfort. All instruments to be employed have been used frequently and without incident with individuals who are using illicit substances. Research interviewers will be trained to be alert to indication of participant discomfort and will discontinue administration of research instruments if a study participant shows discomfort. In such cases occurring at baseline assessment, referral will be made to institutional medical/case management personnel as appropriate. For follow-up assessments, appropriate referral sources will be available to the interviewer in the event of an adverse reaction that requires intervention, and a clinical appointment to deal with this issue will be scheduled if the participant requests.

9.3. Risk/Benefit Ratio

Every effort will be made to minimize the risks to participants in this study. Exclusion criteria, (e.g., medical status), voluntary participation, and careful and constant medical monitoring and protection of confidentiality will help minimize risk to subjects. With regard to study benefits, all participants will receive long-acting naltrexone in prison and will be referred to substance use treatment in the community. In addition, participants will also receive treatment services in prison that may increase entry and retention into community-based treatment following release and thus decrease the likelihood of readdiction and its negative consequences. Results from this study may help determine the utility of administering long-acting naltrexone to inmates in prison with pre-incarceration opioid addiction histories prior to release and continued post-release either at a standard opioid treatment program or utilizing medical mobile treatment.

9.4. Importance of the Knowledge to be Gained

Although progress has been made in the development of effective treatments for opioid addiction that begin during incarceration and continue during the critical period of transition back to the community, further improvement in efforts at treatment entry and engagement is clearly needed. The development of effective treatment strategies for these individuals with histories of pre-incarceration opioid addiction, who are at especially high risk for HIV infection and death from overdose, is of high public health and safety importance. Therapeutic research that has established the effectiveness of XR-NTX in other settings and with other populations, suggests that the proposed intervention holds considerable promise for effectively treating inmates with histories of opioid addiction who are released to the community. It is especially significant that the proposed study is the first to examine naltrexone using mobile health strategies among soon-to-be released prison inmates with regard to a number of post-release outcomes: XR-NTX adherence, opioid use, criminal activity, and HIV risk behaviors.

9.5. Participation of Prisoners

The proposed study involves research on prisoners and therefore is subject to DHHS regulations that provide additional protections for research involving prisoners as research participants. In keeping with their vulnerable status as prisoners, all study participants will receive treatment prior to release (XR-NTX) in prison and in the community and information on how to access various treatment resources in the community. XR-NTX is approved by the FDA for the prevention of relapse to opioid dependence. Both treatment conditions will be receiving study medication. Thus, the study will not employ a “no treatment” control condition, inasmuch as all participants will receive an active substance use treatment (i.e., XR-NTX).

We are sensitive to the possibility that, given the limited financial resources of many prisoners at this point in time, providing cash compensation at baseline could unduly influence inmates to participate in this intervention study. Furthermore, we consider that the treatment that participants receive is ample compensation for the time that they devote to research procedures at baseline. Therefore, no cash compensation will be provided for baseline assessments. Cash compensation will be provided for follow-up interviews conducted following release in recognition of participants' contribution of their time and efforts to the research.

We are also sensitive to ensuring that participants are not being coerced to enroll in the study. Thus, the process of participant enrollment (including participant screening, informed consent, baseline assessment, and medical examinations) will take place without correctional staff present, in private discussions with the research and medical staff of the study. Furthermore, as mentioned above, because of the possibility of coercion when working with prisoners, the study RAs will emphasize that the decision to participate or not will not affect the prisoner's status, privileges, or release date.

9.6. Data and Safety Monitoring Plan

9.6.1. Responsibility for Safety Oversight. As in our past and ongoing clinical trial of prison-initiated methadone and buprenorphine treatment, the Principal Investigator and his study staff, the FRI Institutional Review Board (IRB), and a Data Safety Monitoring Board (DSMB) will provide safety oversight for the project. In addition, an external medical safety monitor (an independent physician with expertise in pharmacotherapy and opioid addiction) will report his/her review of adverse events to the PI, the project's medical staff, and the FRI's IRB. The medical safety monitor will review reports on the study and be informed by the PI of any information that has bearing on the safety of the participants. Finally, the PI will be responsible for conducting a literature search on XR-NTX no less frequently than every six months to identify any emerging research findings that might influence study procedures. Finally, the PI and external medical safety monitor will stay alert to any changes in the labeling of naltrexone.

9.7. Report of Safety-Relevant Information to NIDA

The Principal Investigator is responsible for informing NIDA of any safety-relevant actions taken by the FRI's Institutional Review Board as a result of its regular semi-annual reviews and any special reviews of this project. In addition, the PI will inform NIDA of any major changes in the protocol or its status including: protocol amendments; procedural changes; suspension or termination of subject accrual or of the protocol itself; changes in the informed consent or IRB approval status; and other problems or issues that could have a significant impact on individuals' consent to participate.

9.8. Adverse Event Reporting

As in our other clinical trials, adverse event reporting will follow the usual FRI policy. Serious adverse events (SAEs) include any of the following outcomes for the participant: 1) death; 2) acute life-threatening incidents; 3) hospitalization or the prolongation of a hospitalization; 4) persistent or significant disability or incapacity; or, 5) birth defects. Should they occur, these events may be communicated to the PI by participants and/or staff, or may be observed directly by the PI. SAEs will be reported regardless of whether they are considered study related. Adverse events will be monitored by nursing and medical staff and will include: nasopharyngitis, insomnia, and injection site pain among other more frequently reported reactions. The completed Serious Adverse Event Form will contain: subject's ID#, gender, age, the title and date of the Serious Adverse Event, and narrative explanation. The Serious Adverse Event Report Form tracks how the research staff was notified of the event, dates of consent, study medication, study screening for inclusion/exclusion, study treatment received, outcome of study treatment (e.g., was participant using illicit substances or abstinent, other relevant clinical information), dates and circumstances of the hospitalization/death, whether alcohol or illicit substances were known to be involved, and participant status at last clinical or research contact. In cases of participant death, the report also includes appropriate substantiation from clinic records, as well as copies of the death certificate, autopsy report, or medical record. The Principal Investigator will address whether there is a need to redesign or amend the protocol, and/or to inform current and future subjects of a change in description of risk (in consent form and protocol or other). The Principal Investigator will state whether the event was "expected" and assess its "relatedness" to the study medication or intervention.

9.9. Relatedness

The Principal Investigator ([name]), Medical Co-I ([name]), and Medical Consultant ([name]) will review the information and offer an educated opinion about the relatedness of the event to the study drug.

1 = Definitely – The adverse event:

a) Follows a reasonable temporal sequence from drug administration.

- b) Abates upon discontinuation of the drug (de-challenge).
 - c) Is confirmed by reappearance of the reaction on repeat exposure (re-challenge).
- 2 = Probably – The adverse event:
- a) Follows a reasonable temporal sequence from drug administration.
 - b) Abates upon discontinuation of the drug (de-challenge).
 - c) Cannot be reasonably explained by the known characteristics of the patient's clinical state.
- 3 = Possibly – The adverse event:
- a) Follows a reasonable temporal sequence from drug administration.
 - b) Could have been produced by the patient's clinical state or by other modes of therapy administered to the patient.
- 4 = Remotely – The temporal association between the adverse event and the drug is such that the drug is not likely to have had any reasonable causal relationship with the observed event. The assessment of whether the drug was present prior to the reaction or event could be made by history or by blood level.
- 5 = Definitely not – The adverse event is definitely produced by another known cause, and is not temporally associated with the drug.
- 9 = Unknown – only used while awaiting further information.

In any given case, the Ps will make an initial SAE report to the FRI IRB and the study's medical safety monitor within 48 hours. The PI will submit follow-up reports on participants who have experienced an SAE until the outcome of the event is known. This follow-up information will be reported to the external medical safety monitor and FRI's IRB. A summary of SAEs will be reported to NIDA Program staff through the annual non-competing renewal application mechanism. AEs will be aggregated weekly by nursing staff and reported to the PIs. The PIs will report these AEs in aggregate to the DSMB and IRB on a regular basis.

In addition to the above actions, all regulatory reporting required by the FDA will be closely followed.

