9.13. Criteria for Suspending or Terminating the Study

The study may be modified, suspended, or terminated at the recommendation of the PI, DSMB, or by the FRI IRB in the interests of protecting study participants. The study will be modified to comply with any labeling changes for long-acting naltrexone administration made by its manufacturer or by the Food and Drug Administration. The PI, medical safety monitor, DSMB and/or IRB may recommend modifying, suspending, or terminating the study based on the SAE reports. Trials may be terminated for any one or more of four classes of reasons as determined by the DSMB, as specified below: 1) safety/adverse events; 2) favorable benefit-risk ratio; 3) unfavorable benefit-risk ratio; and 4) inability to answer questions regarding trial efficacy.

9.13.1. Termination Due to Safety/Adverse Events. The DSMB's decision to stop the study with regard to safety/adverse event considerations will be based on the number and severity of study-related adverse events, particularly those determined to be fatal and/or extreme. The study may also be terminated if the DSMB decides that there has been an emergence of an unexpected serious adverse event or events.

9.13.2. Termination Due to Favorable Benefit-Risk Ratio. If the results of an interim analysis of post-release outcome data performed by the DSMB provides compelling evidence for the efficacy of the experimental intervention(s), early termination may be recommended. Such a recommendation would not be made without consideration of other relevant information related to the trial and an assessment of the strength of evidence of benefit.

9.13.3. Termination Due to Unfavorable Benefit-Risk Ratio. If the interim efficacy analysis results show compelling evidence for a lack of clinically relevant outcomes, early termination may be recommended by the DSMB. Such a recommendation would not be made without consideration of other relevant information related to the trial (e.g., safety/adverse event issues).

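### Section 9.9 requires an event to abate on stopping the drug before it can be rated Probably or Definitely related, so a fatal or irreversible event can be rated no higher than Possibly, and one with no other plausible cause fits no final rating

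*Combined protocol and SAP*

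**What the plan says.** Section 9.9 (Relatedness) defines five final ratings and a holding code.

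- **Definitely (1):** reasonable timing after dosing; "Abates upon discontinuation of the drug (de-challenge"; and "Is confirmed by reappearance of the reaction on repeat exposure (re-challenge".
- **Probably (2):** reasonable timing; the same abatement criterion; and "Cannot be reasonably explained by the known characteristics of the patient's clinical state".
- **Possibly (3):** reasonable timing; and "Could have been produced by the patient's clinical state or by other modes of therapy administered to the patient".
- **Remotely (4):** timing that makes a causal role for the drug unlikely.
- **Definitely not (5):** another known cause and no temporal association.
- **Unknown (9):** only while information is awaited.

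No rating says what to do when abatement or re-exposure cannot be observed. The section describes the result as an educated opinion on relatedness to the study drug. Section 9.8, by contrast, asks the Principal Investigator for relatedness "to the study medication or intervention".

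Section 9.13.1 says that the DSMB's safety decision is "based on the number and severity of study-related adverse events, particularly those determined to be fatal and/or extreme". No section says which of the 9.9 ratings make an event study-related.

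**The concern.** De-challenge and re-challenge are useful evidence for reversible reactions. Written as unconditional criteria, they exclude the events for which a causal judgement matters most. A death cannot abate, and neither can permanent tissue loss. The scale therefore holds such events at a low rating, or gives them none, for a reason that has nothing to do with the strength of the causal evidence.

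The protocol expects harms of this kind. Section 9.1.1 states that relapse, including relapse after depot naltrexone is discontinued, "carries a risk of opioid overdose and death because tolerance after a period of abstinence is low". Section 9.2.1 reports that tissue at the injection site can be permanently damaged, and section 9.2.2 describes severe reactions "including tissue death (necrosis). Some of these injection site reactions have required surgery".

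At stake is whether the relatedness rating means anything for fatal and permanent events, in a trial whose first-named safety ground for stopping depends on events being study-related.

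**Working it through.** No figure in the plan bears on this point, so there is nothing to recompute. The check applies the definitions in 9.9 to the events in question and then follows the rating to where it is used.

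**Step 1. Are the lettered criteria joint?** The text prints neither 'and' nor 'or' between them. If any one were enough, the timing criterion, which is the same in ratings 1, 2 and 3, would place every well-timed event in all three at once, and the scale could not separate them. The joint reading is the only one under which these categories differ.

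**Step 2. Apply the scale to a well-timed fatal or irreversible event.**

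| Rating | Plausible other cause exists | No plausible other cause |
|---|---|---|
| Definitely | Fails: cannot abate, cannot be re-challenged if fatal | Fails: same reason |
| Probably | Fails: cannot abate; also has another explanation | Fails: cannot abate |
| Possibly | **Met** | Fails: requires another possible cause |
| Remotely | Not met: timing is reasonable | Not met: timing is reasonable |
| Definitely not | Not met: timing is reasonable | Not met: no other known cause |
| Unknown (9) | Interim use only | Interim use only |

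Abatement alone closes both top ratings. Re-challenge matters only for Definitely and is not needed for the conclusion. In the left column the ceiling is Possibly. In the right column, where the case for the drug is strongest, no final rating fits.

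**Step 3. Match this to the foreseen harms.** Permanent injection-site damage (9.2.1) can fall in either column. Overdose death after discontinuation (9.1.1) arises after the drug is stopped, so abatement on stopping has no meaning for it.

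**Step 4. Follow the rating to the stopping rule.** Section 9.13.1 refers to study-related events without naming ratings.

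- If study-related means Probably or Definitely, the fatal and permanent events that the section singles out cannot qualify.
- If it includes Possibly, those with a plausible other cause qualify, but those without one still have no rating.

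The plan does not say which applies.

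**Step 5. Compare 9.8 with 9.9.** Section 9.8 asks for relatedness to the medication or the intervention; 9.9 supplies a scale for the drug only. Both arms receive the same drug, and the randomised factor is where it is delivered, so the judgement closest to the trial question has no defined scale.

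**The case against.** The strongest case against is that no serious event is lost. Section 9.8 has SAEs reported whatever their relatedness, with supporting records for deaths. Section 9.9 sends an initial SAE report to the IRB and the medical safety monitor within 48 hours. Section 9.10 sends unexpected SAEs to NIDA and the IRB within 24 hours, related or not. Section 9.12 has the DSMB review all SAEs. The opening of 9.13 allows a recommendation to stop on the SAE reports, and 9.13.1 gives unexpected SAEs as a separate ground. Section 6.8 compares adverse events and overdoses by condition without using relatedness at all. This stands, and it limits the consequence. The unexpected-event route helps less than it appears to, since overdose death and necrosis are already described as risks and would probably be classed as expected.

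A reader might go further and infer that fatal events would be left out of the safety stop, or that the DSMB would be reassured whatever happened. The documents do not support that: the board sees every death, and no section ties the 9.9 ratings to 9.13.1.

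A reader might also infer that no event can be rated against mobile or clinic delivery. Section 9.8 contradicts this, because it asks for relatedness to the intervention. What is missing is a scale for that judgement.

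Third, it is fair to say that overdose death after stopping would often stay at Possibly under any sensible scale. Section 9.1.1 notes that relapse risk is common to everyone with this history, so another cause is usually present. That example shows that the abatement criterion does not apply; it does not show that the rating would rise.

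Finally, the rating is called an opinion, 9.8 defers to institutional policy, and the forms in the appendix are not reproduced. Raters may depart from the printed criteria. If they do, ratings will depend on the rater, which is also a reason to correct the text.

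**Conclusion.** The point holds as a defect in the relatedness rating. On the joint reading of 9.9, Probably and Definitely are closed to every fatal or irreversible event, and a well-timed one with no plausible alternative cause has no final rating. This follows from the wording; it is not an estimate of how often it will occur, which the documents do not allow.

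The effect on stopping is a risk whose extent depends on an undefined term. It is greatest if study-related in 9.13.1 means Probably or Definitely, and smaller if Possibly counts. Reporting of SAEs and their review by the DSMB are unaffected, and so is the efficacy analysis.

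The conclusion rests on two assumptions: that the lettered criteria must all be met, and that no form or institutional policy outside the documents already supplies an exception.

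**What to change.** 1. In 9.9, state that de-challenge and re-challenge apply only where they can be assessed. Let an event that cannot abate be rated Probably or Definitely on timing plus the absence of another adequate cause. This also closes the gap between Probably and Possibly.
2. Reconcile 9.9 with 9.8 by applying the same scale a second time on the SAE form, to the intervention (delivery setting) and the study procedures.
3. In 9.13.1, state which ratings count as study-related.

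No new supply of deaths to the DSMB is needed, since 9.12 already has it review all SAEs.

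The cost is protocol and form wording, with no extra visits or staff. The small downside is that some events will be rated as more related than under the current text. The change is best made before ratings accumulate, so that all events are judged on one scale.
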